### **8.4 ADVERSE EVENTS (AES), SERIOUS ADVERSE EVENTS (SAES) AND OTHER SAFETY REPORTING**

The definitions of AEs and SAEs can be found in Appendix 3 ([Section 10.3](#)). The definition of AESI is provided in [Section 8.4.8](#).

The definitions of unsolicited and solicited AEs can be found in Appendix 3 ([Section 10.3](#)).

The Investigator and any qualified designees are responsible for detecting, documenting, and recording events reported by the participant (or, when appropriate, by a caregiver, surrogate, or the participant's legally authorized representative) that meet the definition of an AE or SAE and remain responsible for following up all AEs, considered related to the study IMP or study procedures, or that caused the participant to discontinue the study IMP (see [Section 7](#)). This includes events reported by the participant (or, when appropriate, by a caregiver, surrogate, or the participant's legally authorized representative).

The method of recording, evaluating, and assessing causality of AEs and SAEs and the procedures for completing and transmitting SAE reports are provided in Appendix 3 ([Section 10.3](#)).

#### **8.4.1 Time period and frequency for collecting AE and SAE information**

All AEs (serious or nonserious) will be collected from the signing of the ICF until the EoS visit at the timepoints specified in the SoA ([Section 1.3](#)).

All SAEs and AESI will be recorded and reported to the Sponsor or designee immediately and under no circumstance should this exceed 24 hours, as indicated in Appendix 3 ([Section 10.3](#)). The Investigator will submit any updated SAE data to the Sponsor within 24 hours of it being available.

Investigators are not obligated to actively seek information on AEs or SAEs after conclusion of the study participation. However, if the Investigator learns of any SAE, including a death, at any time after a participant has been discharged from the study, and the Investigator considers the event to be reasonably related to the study IMP or study participation, the Investigator must promptly notify the Sponsor.

#### **8.4.2 Method of detecting AEs and SAEs**

Care will be taken not to introduce bias when detecting AEs and/or SAEs. Open-ended and nonleading verbal questioning of the participant is the preferred method to inquire about AE occurrences.

#### **8.4.3 Follow-up of AEs and SAEs**

After the initial AE/AESI/SAE report, the Investigator is required to proactively follow each participant at subsequent visits/contacts. At the pre-specified study end-date, all SAEs and AEs of special interest (as defined in [Section 8.4.8](#)), will be followed until resolution, stabilization, the event is otherwise explained, or the participant is lost to follow-up (as defined in [Section 7.3](#)). Further information on follow-up procedures is provided in Appendix 3 ([Section 10.3](#)).

#### **8.4.4 Regulatory reporting requirements for SAEs**

- Prompt notification by the Investigator to the Sponsor of an SAE is essential so that legal obligations and ethical responsibilities towards the safety of participants and the safety of a study IMP under clinical investigation are met.
- The Sponsor has a legal responsibility to notify both the local regulatory authority and other regulatory agencies about the safety of a study IMP under clinical investigation. The Sponsor will comply with country-specific regulatory requirements relating to safety reporting to the regulatory authority, Institutional Review Boards (IRB)/Independent Ethics Committees (IEC), and Investigators.
- Serious adverse events that are considered expected will be specified in the reference safety information (IB).
- Investigator safety reports must be prepared for suspected unexpected serious adverse reactions (SUSARs) according to local regulatory requirements and Sponsor policy and forwarded to Investigators as necessary.
- An Investigator who receives an Investigator safety report describing an SAE, SUSAR or any other specific safety information (eg, summary or listing of SAEs) from the Sponsor

will review and then file it along with the IB and will notify the IRB/IEC, if appropriate according to local requirements. It is the responsibility of the Sponsor to assess whether an event meets the criteria for a SUSAR, and therefore, is expedited to regulatory authorities.

#### **8.4.5 Pregnancy**

- Details of all pregnancies in female participants and female partners of male participants will be collected after the start of study IMP and until and until EoS visit.
- If a pregnancy is reported, the Investigator will record pregnancy information on the appropriate form and submit it to the Sponsor within 24 hours of learning of the pregnancy and should follow the procedures outlined in Appendix 4 “contraception and barrier guidance” ([Section 10.4](#)).
- Abnormal pregnancy outcomes (eg, spontaneous abortion, fetal death, stillbirth, congenital anomalies, ectopic pregnancy) are considered SAEs and will be reported as such.
- The participant/pregnant female partner will be followed to determine the outcome of the pregnancy. The Investigator will collect follow-up information on the participant/pregnant female partner and the neonate, and the information will be forwarded to the Sponsor.
- Any post-study pregnancy-related SAE considered reasonably related to the study IMP by the Investigator will be reported to the Sponsor as described in [Section 8.4.4](#). While the Investigator is not obligated to actively seek this information in former participant/pregnant female partner, he or she may learn of an SAE through spontaneous reporting.
- Any female participant who becomes pregnant while participating in the study will discontinue study IMP or be withdrawn from the study.

Prior to continuation of study IMP following pregnancy, the following must occur:

- The Sponsor and the relevant IRB/IEC give written approval.
- The participant gives signed informed consent.
- The Investigator agrees to monitor the outcome of the pregnancy and the status of the participant and her offspring.

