### 7.1 DISCONTINUATION OF STUDY IMP

An individual should discontinue study IMP if any of the following occurs:

- At the request of the participant, ie, withdrawal of consent.
- Pregnancy of a female participant.
- Occurrence of SAE if further participation could jeopardize the safety of the participant.
- Any clinically relevant safety laboratory deviation, including but not limited to [REDACTED]  
[REDACTED]  
[REDACTED]  
[REDACTED] (refer to [Section 7.1.3](#)).
- Worsening of psoriasis requiring intensification of therapy outside of substances permitted in the study (refer to [Section 6.9.2](#) and [Section 6.9.3](#)).
- Any other medically important AE in the judgement of the investigator.

All study IMP withdrawals should be recorded by the Investigator on the appropriate case report form screens for eCRF when considered as confirmed.

In case of premature study IMP discontinuation, see [Section 7.1.1](#) below.

For any participant who fails to return to the site, the Investigator should make every effort to recontact the participant (eg, contact the participant's family or private physician, review available registries or health care database), and to determine his/her health status, including at least his/her vital status. Attempts to contact the participant must be documented in the participant's records (eg, times and dates of attempted telephone contact, receipt for sending a registered letter).

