#### 8.4.8 Adverse events of special interest

An AESI is an AE (serious or nonserious) of scientific and medical concern specific to the Sponsor's product or program, for which ongoing monitoring and immediate notification by the Investigator to the Sponsor is required. Such events may require further investigation to characterize and understand them. AESIs may be added, modified, or removed during a study by protocol amendment.

- Pregnancy of a female participant entered in a study as well as pregnancy occurring in a female partner of a male participant entered in a study with IMP/AxMP;
  - Pregnancy occurring in a female participant entered in the clinical trial or in a female partner of a male participant entered in the clinical trial. It will be qualified as an SAE only if it fulfills one of the seriousness criteria (see Appendix 3 [[Section 10.3](#)]).
  - In the event of pregnancy in a female participant, IMP should be discontinued.
  - Follow-up of the pregnancy in a female participant or in a female partner of a male participant is mandatory until the outcome has been determined (See [Section 8.4.5](#)).
- Symptomatic overdose (serious or nonserious) with IMP/AxMP (see definition of an overdose in [Section 6.8](#)).

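### Protocol 8.4.5 sets conditions for continuing IMP after a pregnancy without saying that the pregnancy must have ended, although every other rule stops dosing

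*Protocol*

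**What the plan says.** Three places in the Protocol stop IMP on pregnancy:

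- Section 7.1 opens its list with "An individual should discontinue study IMP if any of the following occurs", and a female participant's pregnancy is one of the listed events.
- Section 8.4.8, where pregnancy is an adverse event of special interest, states: "In the event of pregnancy in a female participant, IMP should be discontinued".
- Section 8.4.5, in its last bullet, states: "Any female participant who becomes pregnant while participating in the study will discontinue study IMP or be withdrawn from the study".

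The next line of 8.4.5 reads: "Prior to continuation of study IMP following pregnancy, the following must occur". Three conditions follow. The first is "The Sponsor and the relevant IRB/IEC give written approval". The second is signed consent from the participant. The third is "The Investigator agrees to monitor the outcome of the pregnancy and the status of the participant and her offspring".

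Two further provisions bear on the point. Section 7.1.5 allows IMP to be reinitiated after an adverse event only if the selection criteria are still met. Inclusion criterion I 05 b requires that a female participant be neither pregnant nor breastfeeding.

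The SAP treats pregnancy only as an adverse event of special interest (Table 7) and does not resolve the question.

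**The concern.** A site that finds a positive pregnancy test needs one clear instruction. Sections 7.1 and 8.4.8 give one: stop. Section 8.4.5 gives the same instruction and then describes how IMP may be continued, with nothing to show whether this is an exception or a different situation. Neither 7.1 nor 8.4.8 refers to it.

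The phrase about continuation following pregnancy has two possible meanings: dosing goes on after a pregnancy is found, or dosing resumes once the pregnancy is over. The first would expose a pregnant participant and her fetus to an investigational drug, in a trial that requires contraception and excludes pregnant women at entry. The stake is participant safety and clarity of instruction, not the efficacy inference.

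**Working it through.** There is no figure in the plan to reproduce. The check sets the provisions side by side.

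**1. Is the continuation paragraph marked as an exception?** No. The stop rule in 8.4.5 is unconditional, and both of its alternatives end dosing. No connecting word ties the next line to it. The paragraph is current text, and no redaction interrupts it.

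**2. Which meaning do the conditions favour?** Monitoring an outcome that is still to come, and offspring, fits an ongoing pregnancy. The choice of continuation, where 7.1.5 speaks of reinitiating, points the same way. Against this, the word following can mean after the end. With 12 weeks of treatment, a restart inside the treatment period is realistic only after an early pregnancy loss. The ongoing-pregnancy reading is plausible but not settled.

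**3. Does it fit the remaining rules?**

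| Provision | Dosing in an ongoing pregnancy | Restart after the pregnancy has ended |
|---|---|---|
| 7.1, 8.4.8, last bullet of 8.4.5 | Not allowed; no exception | IMP stopped; restart not addressed |
| 7.1.5 with I 05 b | Fails: selection criteria not met | Possible if the criteria are met again |
| Continuation paragraph of 8.4.5 | Can be read as possible with approvals | Can be read as possible with approvals, but no negative test or re-met criteria are named |

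Section 7.1.5 is written for adverse events and does not name pregnancy. Since 8.4.8 defines an event of special interest as an adverse event and lists pregnancy, applying 7.1.5 is reasonable.

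**4. How much dosing could be involved?** Inputs from the schedule of activities (Protocol 1.3): urine tests and IMP intake at Week 4 (Day 29), Week 8 (Day 57) and Week 12 (Day 85), each visit with a window of 3 days either way. Taking the Week 12 visit as the last planned dose, days left = last dose day − test day + 1.

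- Week 4, nominal: 85 − 29 + 1 = 57. With windows: 82 − 32 + 1 = 51 to 88 − 26 + 1 = 63.
- Week 8, nominal: 85 − 57 + 1 = 29. With windows: 82 − 60 + 1 = 23 to 88 − 54 + 1 = 35.
- Week 12: test and last dose fall at the same visit, so 1.

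The ceilings for a positive scheduled test are therefore 63 days at Week 4 and 35 at Week 8, not the nominal 57 and 29. They count the visit-day dose, although footnote k recommends the urine test before dosing, and they allow no time for approvals. An extra test before Week 4, which 8.3.6 permits, could leave more. These figures only show scale; the finding does not depend on them.

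**5. Effect on the primary analysis.** Under Protocol 9.2.2.2, assessments after IMP discontinuation are used, and a missing PASI75 result counts as non-response. Either way a pregnant participant's outcome is already defined.

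**The case against.** The strongest reply is that the paragraph restricts and does not permit. It lists what must happen before any continuation, and it comes after a rule that has already stopped dosing. No site can continue IMP on this text alone: it needs written approval from the Sponsor and the IRB/IEC, and signed consent. Section 7.1.5 with I 05 b then closes the route for a woman who is still pregnant. Pregnancies should also be few, because contraception is required.

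Most of this stands, and it keeps the practical risk low. A reader might infer that the Protocol authorises dosing during pregnancy, or that 8.4.5 flatly contradicts itself. The documents do not support either inference, because the paragraph can also mean restart after the pregnancy has ended.

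What does not stand is that no correction is needed. The approvals make misuse unlikely but do not say which case may be approved. Nothing in 8.4.5 points to 7.1.5 or I 05 b. On the restart reading, the paragraph omits a negative test and re-met eligibility.

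A reader might also infer that deleting the paragraph is enough. Deletion alone would remove the only explicit Sponsor and IRB/IEC requirement for restart after a pregnancy. Restart after an early loss would then fall to 7.1.5, which rests on the Investigator's judgement.

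**Conclusion.** The point holds as an ambiguity in safety wording. Section 8.4.5 can be read as leaving a route to dosing in an ongoing pregnancy, which conflicts with 7.1, 8.4.8, its own stop rule, and 7.1.5 taken with I 05 b. Confidence is high that the wording is unclear and needs correction; it is only moderate that an ongoing pregnancy was meant.

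Severity is low. The documents give no expected number of pregnancies; that there will be few is an assumption based on the contraception requirement. Sample size, type I error control, estimands and analyses are untouched.

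**What to change.** Preferred change to 8.4.5: state that IMP is not given during an ongoing pregnancy, and limit the paragraph to restart after the pregnancy has ended. Restart should require:

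- a negative pregnancy test;
- I 05 b and the other selection criteria met again, with a reference to 7.1.5;
- the existing written Sponsor and IRB/IEC approval and signed consent.

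Add cross-references to this paragraph in 7.1 and 8.4.8.

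Alternative: delete the paragraph and state that IMP is not restarted after a pregnancy. No follow-up is lost, because 8.4.5 already says "The participant/pregnant female partner will be followed to determine the outcome of the pregnancy", and 8.4.8 says that follow-up "is mandatory until the outcome has been determined".

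Cost: one paragraph, two cross-references and a short note to sites. The wording change would go through the amendment and IRB/IEC process in Protocol 10.1.1 and could be included in any other amendment. Visits, sample size and the SAP do not change.

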#### **8.4.6 Cardiovascular and death events**

Cardiovascular events should be reported if they meet AE/SAE criteria. Events with fatal outcome events should be reported as SAEs.

#### **8.4.7 Disease-related events and/or disease-related outcomes not qualifying as AEs or SAEs**

Not applicable.

#### 8.4.8 Adverse events of special interest

An AESI is an AE (serious or nonserious) of scientific and medical concern specific to the Sponsor's product or program, for which ongoing monitoring and immediate notification by the Investigator to the Sponsor is required. Such events may require further investigation to characterize and understand them. AESIs may be added, modified, or removed during a study by protocol amendment.

- Pregnancy of a female participant entered in a study as well as pregnancy occurring in a female partner of a male participant entered in a study with IMP/AxMP;
  - Pregnancy occurring in a female participant entered in the clinical trial or in a female partner of a male participant entered in the clinical trial. It will be qualified as an SAE only if it fulfills one of the seriousness criteria (see Appendix 3 [[Section 10.3](#)]).
  - In the event of pregnancy in a female participant, IMP should be discontinued.
  - Follow-up of the pregnancy in a female participant or in a female partner of a male participant is mandatory until the outcome has been determined (See [Section 8.4.5](#)).
- Symptomatic overdose (serious or nonserious) with IMP/AxMP (see definition of an overdose in [Section 6.8](#)).

#### 8.4.9 Medication errors or misuses of medicinal product

All reports of medication error or misuse in relation to the IMP with or without an AE must be recorded on the corresponding page(s) of the eCRF and transmitted to the Sponsor's representative following standard processes.

A medication error is an unintended failure in the drug treatment process (ie, mistake in the process of prescribing, storing, dispensing, preparing, or administering medicinal products in clinical practice) that leads to, or has the potential to lead to harm to the participant. This includes situations in which a participant was involved or not (eg, even if the error was recognized and intercepted before the participant received or used the product), and whether it resulted in harm to the participant or not.

A misuse refers to situations where the medicinal product is intentionally and inappropriately used, ie, not in accordance with the terms of the marketing authorization or outside what is foreseen in the protocol, by the participant for a therapeutic purpose.

Of note, if a medication error or misuse meets the protocol definition of an overdose, it will be recorded in the overdose page of the eCRF.

#### **8.4.10 Guidelines for reporting product complaints**

Any defect in the IMP must be reported as soon as possible by the Investigator to the monitoring team that will complete a product complaint form within required timelines.

Appropriate information (eg, samples, labels or documents like pictures or photocopies) related to product identification and to the potential deficiencies may need to be gathered. The Investigator will assess whether the quality issue must be reported together with an AE or SAE.

#### **8.4.11 Medical device deficiencies**

Not applicable.

### **8.5 PHARMACOKINETICS**

- Whole blood samples will be collected for measurement of plasma concentrations of SAR441566 as specified in the SoA ([Section 1.3](#)).
- A maximum of 5 samples may be collected at additional timepoints during the study if warranted and agreed upon between the Investigator and the Sponsor. The timing of sampling may be altered during the study based on newly available data (eg, to obtain data closer to the time of peak plasma concentrations or to optimize PK timepoints during the course of the study based on the updated knowledge of drug behavior) to ensure appropriate monitoring.
- Instructions for the collection and handling of biological samples will be provided by the Sponsor in a separate document. The actual date and time of each sample will be recorded. PK samples will be tested by the Sponsor or Sponsor's designee.
- Samples collected for analyses of SAR441566 concentration may also be used to evaluate safety or efficacy aspects related to concerns arising during or after the study.

PK samples could be used for testing analytical method performance such as comparability and incurred sample reproducibility and for possible exploratory analysis of drug metabolites and/or drug interaction. The exploratory data will not be included in the study report but will be kept on file.

SAR441566 concentrations at selected time points after IMP administration will be reported using descriptive statistics. Population PK and PK/PD approaches will be used for the estimation of PK parameters such as  $C_{max}$ ,  $t_{max}$ , and  $AUC_{0-\tau}$ , and for possible exposure-response analyses if appropriate. These results will be presented in a separate stand-alone report.

Drug concentration information that would unblind the study will not be reported to investigative sites or blinded personnel until the study has been unblinded.

For China, see [Section 10.7.1](#) for details.

## 8.6 PHARMACODYNAMICS

See [Section 8.7 Genetics](#) and [Section 8.8 Biomarkers](#) for a description of pharmacodynamic parameters.

[figure not shown]
[figure not shown]
Details on processes for collection and shipment and destruction of these samples can be found in the laboratory manual. Results will be presented in reports separate from the clinical study report (CSR). See Appendix 5 ([Section 10.5](#)) [Genetics] for information regarding genetic research.

Genetic analyses will not be done for participants enrolled in China ([Section 10.7.1](#)).

## 8.8 BIOMARKERS

Whole blood, plasma and serum blood samples will be collected to assess the [REDACTED] of systemic inflammation associated to psoriasis, as well as disease markers and their correlation with clinical response. Samples will be collected pre-IMP dose and at the timepoints specified in the SoA, as detailed in a laboratory manual provided separately to sites.

Quantitative analysis of soluble blood proteins associated with psoriasis and/or SAR441566 activity will be performed in serum or plasma including but not limited to:

- IL-17A, IL-17F, IL-22, IL-19,   IL-17A and IL-17F are

released by skin infiltrating immune cells and are commonly accepted as key disease drivers. IL-22 is released by lesional psoriatic skin, whereby high concentrations correlate with disease activity. IL-19 is a component of IL-23/IL-17 cascade, which is increased in psoriasis and correlated to PASI.

Soluble protein biomarkers will be assessed through standardized methods. Instructions for the collection and handling of the biological samples will be provided in a separate document.

Whole blood samples will also be collected for [REDACTED]  
[REDACTED]  
[REDACTED]  
[REDACTED]

Blood samples will be collected for [REDACTED]

With specific consent, optional blood samples will be collected for future biomarker analysis and/or retrospective safety follow-up, potentially including but not limited to [REDACTED]  
[REDACTED] exploratory analysis reflecting effects of SAR441566 and/or to identify markers potentially predictive of clinical response. Participation is optional. Participants who do not wish to participate in the research may still participate in the study.

Analyses may also seek to identify which markers are associated with clinical response to SAR441566, or can be predictive of clinical response, or correlate to clinical response and clinical features.

For China, see [Section 10.7.1](#) for details.

